#### Handling of Missing Data

This is a prospective pilot study and all patients will be treated and monitored at Mayo Clinic in Rochester, MN. All clinically relevant data will stored in the Mayo Clinic electronic medical record (Epic). Data queries will be performed at the conclusion of the study to recover any missing data.

#### **Primary Hypothesis:**

The primary hypothesis that arrhythmogenesis and SCD risk in this population is influenced by amyloid cardiomyopathy stage rather than reduced left ventricular ejection fraction, which is often a marker of late disease and increased mortality due to heart failure, and that SCD due to asystole, rather than VA which could be treated with ICD. Conduction system disease causing heart block, atrial arrhythmias and VA leading to SCD may occur earlier in the disease process and treatment of AF, VA, and heart block could improve both morbidity and mortality.

A Student's t-test will be used to compare differences in arrhythmia burden between the patients in the two groups (early stage I-II vs stage III either with any implanted cardiac device).

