Despite high risk of SCD, appropriate risk stratification in amyloid cardiomyopathy is lacking. Traditional risk stratification with decreased ejection fraction (<35%) commonly

applied to ischemic cardiomyopathy is not useful in amyloid cardiomyopathy where decreased ejection fraction is a late finding and indicative of advanced disease and increased mortality due to low output and pump failure. Recent studies have cast increasing doubt on the wisdom of generalizing decreased ejection fraction as a risk stratifier for SCD in patients with heart failure due to other causes, specifically those with non-ischemic cardiomyopathies(23) and heart failure with preserved ejection fraction (24). At this time, patients with amyloid cardiomyopathy are without appropriate risk stratification metrics and are at risk for inadequate treatment and at increased risk for SCD.

The prognostic value of non-sustained VA, another traditional risk factor for SCD in ischemic cardiomyopathy, is also controversial in amyloid cardiomyopathy. Long term outpatient monitoring of both supraventricular and ventricular arrhythmias for prognostic implications in relation to other diagnostic modalities is instrumental in understanding the disease process and providing appropriate therapy.

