Currently, the balance of data does not support ICD implantation in amyloid cardiomyopathy (7). However, some studies have demonstrated that ventricular arrhythmias resulting in SCD can be successfully treated with defibrillation, hypothesizing that this treatment may be more successful in earlier stage disease (8,26,27). SCD in late stage disease has been hypothesized to be due to electromechanical dissociation or bradycardia mediated asystole for which an ICD would not be beneficial (25)(8,18). The Mayo clinic staging system based on cardiac biomarkers has been validated and is used to stratify severity of disease (early vs late stage) in TTR-wt cardiomyopathy. The reported 4 year survival estimates of patients with Mayo stage I (TnT <0.05ng/ml and NT BNP <3000 pg/mL), II (either TnT >0.05 ng/ml or NT BNP >3000 pg/mL), and III (TnT >0.05 ng/ml and NT BNP >3000 pg/mL) TTRwt amyloidosis was 57%, 42%, and 18%, respectively (28). Those patients with advanced amyloid cardiomyopathy may have estimated survival less than a year due to heart failure and should be excluded from ICD whereas those with earlier stage may still have added survival benefit. We hypothesize that the occurrence and treatibility of ventricular arrhythmias is dependent on disease progression and may be a phenomena of earlier stage disease. Monitoring at all stages of CA disease to understand arrhythmia risk at each stage is instrumental in understanding the true prevalence and treatment of arrhythmias.

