#### **1.4.3** Potential Benefits

We hypothesize that arrhythmogenesis and SCD risk in this population is influenced by CA stage rather than reduced left ventricular ejection fraction, which is a marker of late disease and increased mortality due to heart failure, bradycardia, or asystole, rather than SCD due to VA. The purpose of this study is to identify TTR-wt cardiac amyloidosis patients at risk for bradycardia or SCD due to VA who may benefit from PPM or ICD, and to determine whether monitoring may be appropriate as standard of care to identify the subgroup of patients who will benefit from PPM or ICD.

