#### 2.2 Secondary Objective

The secondary goal is to assess arrhythmogenesis in relation to stage of cardiac amyloidosis

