#### 4.1 Inclusion Criteria

- 1. Cardiac biopsy or technetium pyrophosphate scintigraphy confirmed patients
- 2. Stage I, II, and early and late stage III in numbers as described, irrespective of EF or NYHA functional class
- 3. Patients aged 18 -85, both genders and of all races and ethnicities.
- 4. Patients must be competent to give informed consent.
- 5. Patients must be able to have the Biomonitor 3 implanted.
- 6. Amyloid stages I-III patients with existing implantable cardiac devices such as pacemakers or defibrillators

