#### 6.2 Statistical Methods

#### **Descriptive Statistics**

Univariate descriptive statistics and frequency distributions will be calculated, as appropriate for all variables. Baseline values for demographic, clinical, and outcome variables (primary and secondary) will be tabulated for the two groups. These analyses will help identify baseline clinical characteristics that may be associated with risk of sudden cardiac arrest or bradycardia requiring pacemaker implantation.

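### The primary hypothesis sets stage against reduced LVEF, but the only planned test is an unadjusted comparison of arrhythmia burden by stage, so the LVEF half of the claim is untested

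*Combined protocol and SAP*

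**What the plan says.** The hypothesis appears twice. Section 6.2, under Primary Hypothesis, says that "arrhythmogenesis and SCD risk in this population is influenced by amyloid cardiomyopathy stage rather than reduced left ventricular ejection fraction". Section 1.4.3 says the same in nearly identical words: "arrhythmogenesis and SCD risk in this population is influenced by CA stage rather than reduced left ventricular ejection fraction". Both wordings compare two predictors.

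The analysis follows in Section 6.2: "A Student's t-test will be used to compare differences in arrhythmia burden between the patients in the two groups". The groups are stage I-II and stage III. No covariate is named, and within Section 6 LVEF occurs only in the wording of the hypothesis.

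Two other places come near the question:

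- Section 6.2, Descriptive Statistics: "Univariate descriptive statistics and frequency distributions will be calculated, as appropriate for all variables". Baseline and outcome variables are tabulated for the two groups, and the section adds that this will help identify baseline characteristics associated with sudden cardiac arrest or with bradycardia that needs a pacemaker.
- Specific Aim 3 in Section 2 looks for imaging or clinical predictors of sudden cardiac arrest.

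Neither names a test or a model, and neither has arrhythmia burden as its outcome.

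The t-test does match Section 2.2: "The secondary goal is to assess arrhythmogenesis in relation to stage of cardiac amyloidosis".

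**The concern.** A claim that one factor matters and another does not needs an analysis that contains both. This is more than a formality here, because the protocol expects the two to go together. Section 1.4.1 says that "decreased ejection fraction is a late finding and indicative of advanced disease and increased mortality", and Section 4.1 admits patients "irrespective of EF or NYHA functional class", so LVEF is free to differ between the stage groups.

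The ambiguity runs both ways:

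- If burden is higher in stage III, the result fits stage acting apart from LVEF, and equally fits LVEF carrying the difference.
- Section 1.4.1 also hypothesises that the occurrence and treatability of ventricular arrhythmia "is dependent on disease progression and may be a phenomena of earlier stage disease". If low LVEF raises burden in stage III, a true early-stage excess could be cancelled and the t-test would show little.

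What is at stake is the interpretation of the pilot and what it hands to the larger trials that Section 6.1 says it will inform. Care within the study is not affected.

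**Working it through.** **The plan's own figures.** There are none to reproduce. Section 6.1 gives no significance level, power, effect size or SD, and the 50 patients are not derived. The finding itself rests on setting the hypothesis beside the analysis; the arithmetic below only illustrates its possible size.

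**Inputs.** From Section 4: 25 patients per group. Assumed, because the documents are silent: two-sided 5% level; burden normal with within-group SD 1; mean LVEF lower in stage III by a gap of 0.2 to 1.0 SD; within-group LVEF-burden correlation ρ of 0.1 to 0.7, lower LVEF meaning more burden.

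**1. Burden driven by LVEF only.** The group difference is gap × ρ. The t-test has 48 degrees of freedom and noncentrality gap × ρ / √(2/25), where √(2/25) = 0.283. For example, gap 0.8 and ρ 0.5 give 0.40/0.283 = 1.41, so 28% rejection. Gap 1.0 and ρ 0.7 give 0.70/0.283 = 2.47, so 68%.

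| LVEF gap (SD) | ρ 0.1 | 0.2 | 0.3 | 0.5 | 0.7 |
|---|---|---|---|---|---|
| 0.2 | 5% | 5% | 6% | 6% | 8% |
| 0.5 | 5% | 6% | 8% | 14% | 23% |
| 0.8 | 6% | 9% | 13% | 28% | 49% |
| 1.0 | 6% | 11% | 18% | 41% | 68% |

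In simulation, a linear model containing stage and error-free LVEF rejects for the stage term in about 5% of trials.

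**2. Masking.** Let stage I-II truly be 0.8 SD higher, with ρ = 0.5. The observed difference is 0.8 − gap × ρ.

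- Gap 0.2: 0.70 SD. The t-test detects it in 68% of trials, the adjusted model in 88%.
- Gap 0.8: 0.40 SD. The t-test detects it in 28%, the adjusted model in 83%.

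If burden is lognormal and analysed on the raw scale, the adjusted figures drop to about 69% and 65%. The model still does better than the t-test, but by less than normal data suggest.

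**3. Cost of adjusting when LVEF is unrelated to burden.** The stage standard error grows by about √(1 + gap²/4), which is 1.08 at gap 0.8. For a 0.8 SD stage effect, power falls from 79% to 78%, 76%, 72% and 69% at gaps 0.2, 0.5, 0.8 and 1.0 SD (normal data). On raw lognormal data the comparison at gap 0.8 is about 60% against 51%.

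**4. What the LVEF term can show.** With LVEF as the only driver and ρ of 0.1, 0.2 and 0.3, its coefficient is non-significant in about 89%, 72% and 44% of trials. A non-significant LVEF term is therefore not evidence of no effect.

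**5. Sudden cardiac death.** Section 1.4.1 gives 4-year survival of 57%, 42% and 18% for stages I, II and III. At an assumed constant hazard, expected all-cause deaths in 25 patients over six months are 25 × (1 − S^(0.5/4)) = 1.7, 2.6 and 4.8. That is 1.7 to 2.6 deaths in the stage I-II group and 4.8 in stage III. Sudden deaths are a subset of these, too few for a two-predictor model.

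**The case against.** The best defence is that this is a pilot whose hypothesis is worded more widely than its analysis. Outside the hypothesis wording, no aim, objective or endpoint names LVEF; the clause reads partly as background carried over from Section 1.4.1; and the t-test serves the secondary objective as written. This stands as far as it goes. It is why rewording is a complete remedy, and why the consequence is limited to interpretation. It does not make the hypothesis, as worded, testable by the plan. The only power disclaimer of this kind, in Section 1.4.1, concerns tafamidis effects, not the LVEF contrast.

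It can also be said that the descriptive tables and Aim 3 cover the matter. The plan does intend a descriptive look at baseline characteristics in relation to arrest and bradycardia needing a pacemaker. But tables split by stage can show at most that LVEF differs between the groups, not how LVEF relates to burden.

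The adjusted model has limits of its own. It will often be unable to settle the contrast with 50 patients (step 4 of the working). A continuous LVEF term is also not the same question as reduced LVEF, for which Section 1.4.1 mentions a threshold of 35%. Both points stand, and they are reasons to call the model exploratory.

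A reader might infer from the table that the planned t-test has an inflated false-positive rate. The documents do not support that. If LVEF falls because stage advances, a stage difference carried by LVEF is still a real stage difference; only its attribution is open.

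**Conclusion.** The concern holds: followed exactly, the plan can support a statement about burden by stage but not one that places stage above LVEF. This conclusion comes from the text and does not depend on the simulations.

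Its practical size is unknown and runs from negligible to large. The 5% to 68% range rests wholly on assumed LVEF gaps, correlations, a 5% level and normal burden. It would be too strong to say that a stage difference in this study will be due to LVEF, since the documents give neither the LVEF gap between stages nor any LVEF-burden relation. It would also be wrong to say that LVEF goes uncollected: Section 5 lists a clinical echo within six months of enrollment.

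The plan should be changed before analysis, while the choice can still be pre-specified.

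**What to change.** Either of two changes is enough.

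**(a) Add one exploratory model to Section 6.2 and keep the t-test.**

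- Define the burden variable first. Section 5 lists several arrhythmias of interest without a unit or a composite, and the t-test needs this definition as much as the model does.
- Model that variable on stage group and baseline LVEF, on a scale suited to skewed data. Report both coefficients with 95% confidence intervals, and the stage-LVEF association.
- Describe the adjusted stage coefficient as the stage association not shared with LVEF. Do not read a non-significant LVEF term as absence of an effect. State that continuous LVEF does not answer the threshold question.
- Take LVEF from the echo closest before each patient's monitoring window, and flag patients who have none. Where a six-month retrospective window lies wholly before enrollment, an echo within six months of enrollment cannot precede its start, so an older one must be sought. Section 5 mentions retrospective windows for stage III device patients only, but Section 4.1 admits device patients in stages I-III; the plan should say to whom this applies.
- Limit any stage-versus-LVEF statement to burden. Report sudden deaths and resuscitated arrests descriptively, each with stage and LVEF.

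Cost: plan wording, some record searching at a single centre, and power. If LVEF is unrelated to burden, power for a 0.8 SD stage effect falls from 79% to about 72% at a 0.8 SD LVEF gap (normal data). Keeping the t-test limits that loss.

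**(b) Reword Sections 1.4.3 and 6.2 as a stage comparison only, in line with Section 2.2.** This needs no new data or analysis, but gives up the LVEF claim.

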#### 4.4 Early Withdrawal of Subjects

#### 4.4.1 When and How to Withdraw Subjects

Patients may withdraw at any time from the study. Reason for withdraw may include but are not limited to adverse events, progression of disease requiring withdrawal or simply the patient's decision to withdraw.

If a subject does withdraw, that subject will be replaced according to the originally assigned group to permit enrollment of 50 patients complete the study.

Patients may be withdrawn from the study by the investigators if an insertable monitor requires emergent removal. Reasons for removal include, but are not limited to: patient death; loss of sensing; inability to program/interrogate the inserted monitor; infection, battery end of life (normal or premature); system upgrade; physician preference for another insertable monitor model; and/or other reason(s) which may or may not be known to the insertable monitor manufacturer. Complications related to other portions of the insertable monitor system (i.e., patient) may also result in insertable monitor removal. The table below summarizes some of the more common reasons for insertable monitor removal.

Source	Cause	Possible Effect
Battery	Premature depletion or other cause(s) resulting in excessive battery current drain.	Inability to program/interrogate; sensing difficulty.
Circuitry	Electrical parameter changes due to shorts, opens, or component parametric drift Electromagnetic Interference (EMI) from large power tools, industrial equipment, electrocautery, defibrillation, radiation therapy, RF ablation therapy, etc.	Reversion to "Elective Replacement" or electrical reset parameters; inability to program/ interrogate; other damage to circuit components resulting in permanent or temporary parameter changes.
Patient	Normal medical complication	Infection
	Body rejection phenomena	Fluid accumulation; migration; erosion.
	Physician preference	Upgrade to an implantable cardiac pacemaker or implantable cardioverter defibrillator.

If the device is removed due to need for a pacemaker or implantable cardioverter defibrillator the patient will continue to be monitored via the pacemaker or defibrillator as per clinically indicated standard of care monitoring protocol and intervals.

If a subject chooses to withdraw from the study, and requests the monitor to be explanted prior to the end of the 6 month study monitoring period, there will be no further follow up.

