#### 4.7 Subject Compliance Monitoring

All patients will undergo Home Monitoring of their device. By default, the Biomonitor 3 will transmit all data and a daily trend report between 1:00 A.M. and 2:00 A.M. daily. BIOTRONIK's Home Monitoring system is also designed to notify clinicians in less than 24 hours of changes to the patient's condition or status of the inserted device. Updated data may not be available if:

- The patient's CardioMessenger is off or damaged and is not able to connect to the Home Monitoring Service Center.
- The CardioMessenger cannot establish a connection to the inserted device.
- The telephone and/or Internet connection do not operate properly
- The Home Monitoring Service Center is off-line (upgrades are typically completed in less than 24 hours)

These updates will help to assist the subject to make the necessary changes so that data can be transmitted and they are not lost to follow up.

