#### Home Monitoring for arrythmias

Telemetry tracings from the implantable monitor will be reviewed monthly or whenever an event occurs and/or a patient transmits data due to symptoms via remote assistance.

Default transmission is data sent daily between 1:00AM and 2:00AM regardless of events. If there is a problem with transmission the device will alert the physician within 24 hours and this will help to maintain compliance of transmission.

If no events occur the device will be interrogated prior to explantation at the end of the 6 month monitoring period.

The study investigators will be responsible for telemetry review. The patient's treating cardiologist will be notified of events of clinical significance. Treatment of the arrhythmias will be based on current clinical guideline recommendations for bradycardia and VA. Clinical follow up will occur via standard of care clinical visits.

SCD is defined as sudden and unexpected death within 1 hour of cardiac symptoms in the absence of progressive cardiac deterioration, unexpected death during sleep, or unexpected death within 24 hours after last being seen alive. Study participants who experience SCD while monitored and are successfully resuscitated after life-threatening VA will receive an implantable cardioverter defibrillator based on current clinical guidelines. These and other arrhythmic events recorded by the implantable monitor, or SCD that cannot be successfully resuscitated, will be considered events of interest and NOT adverse events, as these are not a consequence of monitoring via the implantable device.

At the end of the 6 month monitoring period, the device will be explanted. Participants will be offered the choice to retain the device until battery end of life if clinically indicated. However, patients who opt to continue monitoring will be informed that their insurance

company will be billed for clinically indicated monitoring and explantation outside the study time frame.

For any patients who expire during the study monitoring period, the terminal rhythm of participants who die will be reviewed remotely via the Biotronik website irrespective of whether the monitor can be retrieved. Patients will be informed of this possibility during the consent process.

For stage III patients with existing ICD or pacemakers, rhythm monitoring will be obtained from the device over a 6 month timeframe and may be retrospective if applicable.

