Patients with existing implantable cardiac devices will undergo a device interrogation at enrollment and at the end of the 6 month monitoring period. If available, records from interim routine and unscheduled clinical device interrogations during the 6 month monitoring period be requested for review by the investigators.

Routine clinical follow up will be continued including clinically indicated ECHOs, ECGs,

I imeline for testing:		
Tests		
	At baseline (clinical echo within 6 months of enrollment date) and scheduled as clinically	
ECHO- TTE	indicated	
Biopsy or technetium pyrophosphate scintigraphy	As clinically indicated, inclusion criteria for the study	
pyrophosphate schutgraphy		
	Clinically indicated at baseline (within 6 months of	
EKG	enrollment) and when clinically indicated	
MRI with T1	When clinically indicated	
Cardiopulmonary exercise		
test	When clinically indicated	
Biomonitor 3	Monitored with a clinically significant event	
NT proBNP	When clinically indicated, inclusion criteria for the study based on clinically indicated testing	
	When clinically indicated, inclusion criteria for the	
Troponin T	study based on clinically indicated testing	
Labs: CBC, Basic Metabolic		
Panel, Mg	When clinically indicated	
Urine pregnancy	At baseline for women of child bearing potential	

Timeline for testing:

and blood work.

An insertable monitor may be removed emergently at the investigator's discretion at any time subsequent to an implant procedure. Reasons for removal include, but are not limited to: patient death; loss of sensing; inability to program/interrogate the inserted monitor; infection, EOS (normal or premature); or other reason(s). Complications related to other portions of the insertable monitor system may also result in insertable monitor removal.

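### The only named test compares arrhythmia burden by stage across two recording routes, with the mix of routes by stage uncontrolled and paced patients unable to show bradycardia

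*Combined protocol and SAP*

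**What the plan says.** The Primary Hypothesis text in section 6.2 compares "differences in arrhythmia burden between the patients in the two groups (early stage I-II vs stage III either with any implanted cardiac device". This is the only named test. Section 6.3 analyses any enrolled subject with a device implanted and makes no split by device type.

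The protocol describes two ways of obtaining rhythm data.

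- **Biomonitor 3.** By default "the Biomonitor 3 will transmit all data and a daily trend report" (section 4.7). "Telemetry tracings from the implantable monitor will be reviewed monthly or whenever an event occurs", and also when a patient sends data because of symptoms (section 5, Home Monitoring).
- **Existing pacemaker or ICD.** "Patients with existing implantable cardiac devices will undergo a device interrogation at enrollment and at the end of the 6 month monitoring period". Between those two readings the investigators ask for whatever clinic interrogation records exist. The same section says: "For stage III patients with existing ICD or pacemakers, rhythm monitoring will be obtained from the device over a 6 month timeframe", and allows that window to be retrospective.

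Inclusion criterion 6 in section 4.1 is not limited to stage III: "Amyloid stages I-III patients with existing implantable cardiac devices such as pacemakers or defibrillators". A patient whose monitor is removed because a pacemaker or ICD is needed changes route: "the patient will continue to be monitored via the pacemaker or defibrillator as per clinically indicated standard of care monitoring protocol and intervals" (section 4.4.1).

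Section 5 lists bradycardia below 35 bpm and heart block among the arrhythmias of interest. Sections 6.2 and 6.3 contain no stratification or adjustment by route, no sensitivity analysis, and no definition of burden common to both routes.

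**The concern.** Recording route may be tied to the factor under test. Section 5 writes device-based monitoring for stage III, section 4.1 admits such patients at any stage, and enrolment fixes only 25 patients per stage group. The number on each route within a group is left to chance and referral.

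Route also affects what can occur, as well as how it is read. As a matter of clinical reasoning, a working pacemaker prevents a rate below 35 bpm and can mask heart block. A patient already paced for conduction disease would score near zero on the feature that Aim 1 sets out to measure. The group with more pacemakers would look less affected by bradycardia while having more known conduction disease. For AF and ventricular arrhythmia the documents give no basis for a direction.

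Section 6.1 says the study is to assess the true arrhythmic burden and to form the basis of larger trials. A small sample widens the interval around the stage contrast; an unbalanced mix of routes shifts the contrast itself, and later trials would inherit that shift.

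**Working it through.** The plan states no alpha, power, effect size or SD, so there is no figure of its own to reproduce. The checks below are illustrations.

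**Inputs.** From the protocol: 25 patients in stage I-II and 25 in stage III (section 4). Assumed: the numbers on existing devices; k, the count recorded on an existing device relative to Biomonitor 3; a mean count of 4; CV 1 or 1.5; two-sided 5% level; equal true burden in the two groups.

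**1. Recorded ratio, stage III to stage I-II.** With shares q3 and q12 on existing devices:

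ratio = (1 - q3 + q3·k) / (1 - q12 + q12·k)

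- 10 v 2 (q3 = 0.40, q12 = 0.08): k = 0 gives 0.60/0.92 = 0.65; k = 0.5 gives 0.80/0.96 = 0.83; k = 2 gives 1.40/1.08 = 1.30.
- 5 v 0 (q3 = 0.20, q12 = 0): 0.80, 0.90 and 1.20.
- Equal shares: 1.00 for every k.

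The case k = 0 is an upper bound. It applies to bradycardia only, with every existing device pacing.

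**2. Rejection rate of the t-test with no true difference** (simulated negative binomial counts, pooled-variance t-test):

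| On existing devices | CV | k = 0 | k = 0.5 | k = 2 |
|---|---|---|---|---|
| 10 v 2 | 1 | 20% | 8.5% | 10-11% |
| 10 v 2 | 1.5 | 13% | 6% | 6-7% |
| 5 v 0 | 1 | 10% | 6% | 7% |
| 5 v 0 | 1.5 | 7% | 5% | 5% |

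A different model (normal data, existing devices in stage III only, recorded burden shifted by 0.5 to 1.0 SD) points the same way. The false difference is share × shift. A 20% share gives 0.1 to 0.2 SD and 6.2% to 9.3% rejection; a 40% share gives 0.2 to 0.4 SD and 10.0% to 24.3%. With 40% in both groups the bias is zero.

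**3. Does restricting to Biomonitor 3 cure it?** Section 1.4.1 says pacemakers are placed on standard guideline criteria, so having one marks conduction disease. Take 10 v 2, equal true burden, exponential burden, and an assumed correlation between burden and having a device:

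| Correlation | Biomonitor 3 only | Pooled, k = 0 | Pooled, k = 0.5 |
|---|---|---|---|
| 0.3 | 0.86 | 0.56 | 0.80 |
| 0.5 | 0.77 | 0.50 | 0.77 |
| 0.8 | 0.61 | 0.40 | 0.74 |

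The true ratio is 1.00 throughout. Restriction is milder than pooling at k = 0, but at k = 0.5 it can be worse.

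**4. Precision.** The 95% half-width in SD units is t(0.975, df)·√(1/a + 1/b).

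- 25 v 25: 2.011 × √0.0800 = 0.569.
- 15 v 23 (Biomonitor 3 only): 2.028 × √0.1101 = 0.673; 0.673/0.569 = 1.18.
- Stratified by route: information 9.079 (15 v 23) + 1.667 (10 v 2) = 10.746; 2.012/√10.746 = 0.614; 0.614/0.569 = 1.08.

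**The case against.** The strongest reply has four parts.

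**This is a pilot with no stated alpha or power.** That is so, and the rejection rates above are only a scale. A shifted estimate is still a problem when the pilot is meant to inform later trials.

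**The mix may balance.** This stands. Section 4.1 admits existing devices at all stages, and the month-6 interrogation sentence has no stage limit. A reader might infer from the stage III wording in section 5 that the groups are recorded by different routes. The documents do not establish that. They leave the balance unknown.

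**Two interrogations need not mean less data.** A reader might infer that existing devices record less because they are read less often. The documents do not say so: interim records are requested where available, such devices may store rhythm between interrogations, and nothing in the text compares the accuracy of the two routes. The case therefore does not rest on reading frequency. Its firmest part is that pacing prevents the event being counted, which end-of-study data queries cannot recover.

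**The plan covers part of this.** Section 6.2 tabulates baseline variables by group, which could include existing devices, and section 3.3 asks for indication and pacing frequency at pacemaker implantation. Neither is tied to the burden comparison.

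Inclusion criterion 5 requires that a Biomonitor 3 can be implanted, which might suggest that everyone has one. Section 5 nevertheless takes rhythm data for stage III patients with existing devices from those devices.

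**Conclusion.** The concern holds. One t-test pools two recording routes, the mix by stage is uncontrolled, and no analysis separates them. If the mix differs by stage, the contrast partly reflects how burden was recorded. On the assumed 10 v 2 split the recorded ratio is 0.65 to 1.30 and the test rejects in about 6% to 20% of trials. With 5 v 0 it rejects in about 5% to 10%, and with a balanced mix there is no bias. Shares, k, mean and CV are all assumptions, and the 20% figure applies to bradycardia only. The direction is clear for bradycardia and open for AF and ventricular arrhythmia.

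A reader might go further and conclude that the main comparison should be restricted to Biomonitor 3 patients. The documents do not support that as a cure: pacemakers follow guideline criteria, so restriction removes patients with known conduction disease, possibly unevenly by stage. It is useful as a sensitivity analysis. The point affects interpretation of the stage contrast; it does not bear on safety.

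**What to change.** In section 6.2:

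1. Tabulate by stage group the route (Biomonitor 3, existing pacemaker, existing ICD, switched during study), whether the window was prospective or retrospective, and patient-months on each.
2. Report burden separately by arrhythmia type, and by route within stage. Beside the pooled comparison, give a route-stratified comparison and a Biomonitor 3-only comparison as sensitivity analyses. State that the latter is itself subject to selection, because having a pacemaker marks conduction disease.
3. For patients entering with a pacemaker, report its indication and pacing frequency as baseline conduction disease. Do not count them as zero in the bradycardia and heart block comparison.
4. Report a patient who receives a pacemaker or ICD during the study as having had a conduction or arrhythmia event. Do not rely on a per-month rate cut at the switch, because the outcome triggers the switch: one event followed by a pacemaker at two weeks scores 1/0.5 = 2 per month, against 1/6 = 0.17 for one event over six months.
5. Keep all patients for the endpoints in sections 3.2 and 3.3.

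The cost is text and tables, using data the protocol already collects, with no extra visit, procedure or patient. On the assumed 10 v 2 split, the interval is about 8% wider for the stratified result and 18% wider for the Biomonitor 3-only result.
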